#### Severity Definition of Adverse Events:

Mild - A type of AE that is usually transient and may require only minimal treatment or therapeutic intervention. The event does not generally interfere with usual activities of daily living.

This document is confidential.

## Statistical Analysis Plan

Sponsor: Zogenix International Limited; Protocol No.: ZX008 Study 2 (ZX008-1501 and ZX008-1502)

---

Moderate - A type of AE that is usually alleviated with additional specific therapeutic intervention. The event interferes with usual activities of daily living, causing discomfort but poses no significant or permanent risk of harm to the research participant.

Severe - A type of AE that interrupts usual activities of daily living, or significantly affects clinical status, or may require intensive therapeutic intervention.

CDISC SDTM Severity Intensity Scale for Adverse Event Terminology

Any missing severity will be imputed as "severe."

The original terms used by the investigators in the eCRFs to identify AEs will be coded using the most recent version of the MedDRA implemented by the sponsor at the end of the study.

### Overview of Adverse Events:

The number and percent of patients with at least one of the following events will be summarized in an overall summary table:

- TEAE.
- Serious TEAE
- Related TEAE
- Related serious TEAE.
- Severe TEAEs
- Adverse events of special interest
- TEAEs that lead to death
- TEAE leading to discontinuation of study treatment

The percentage denominator for the calculation of percentage will be the number of subjects in the SAF.

### Incidence of Treatment Emergent Adverse Events

The following summaries will display the number and percentage of subjects with an adverse event as well as the corresponding number of events by system organ class (SOC) and preferred term (sorted alphabetically):

- All TEAEs
- Serious TEAEs
- TEAEs by Maximum Severity
- Study Drug Related TEAEs
- All AEs that lead to premature discontinuation from the study

Additional summary tables will tally the number and percent of subjects in each treatment group who experience an AE that occurs in at least 2%, and at least 5%, of subjects. The summary will be presented by preferred term in decreasing order of incidence.

This document is confidential.

**Statistical Analysis Plan**

Sponsor: Zogenix International Limited; Protocol No.: ZX008 Study 2 (ZX008-1501 and ZX008-1502)

A table will be provided for TEAEs (preferred term) where the percentage of subjects in a ZX008 arm who experience the event exceeds the percentage of subjects in the Placebo group with the event and occurs with a frequency of at least 2%.

No inferential statistical methods (i.e., methods that yield p-values) will be used to compare treatment groups on the frequency or severity of AEs.

These summaries will be provided for the T+M period.

Additionally, the following listings will be produced for all enrolled subjects:

- All AEs, events considered to be TEAE will be identified in the listing
- Serious AEs
- AEs that lead to premature discontinuation from the study
- Deaths

**Adverse Events by Age and Gender**

The following summary tabulations will be provided to explore the incidence of AEs within age and sex subgroups:

- All TEAEs by Age (<6 years, ≥6 years)
- All TEAEs by Sex (Females, Males)

**Adverse Events by Concomitant Medication Usage**

The following summary tabulations will be provided to explore the incidence of AEs by concomitant medication usage:

- Valproate
- Clobazam
- Topiramate

**Adverse Events by Contry**

The following summary tabulations will be provided to explore the incidence of AEs by contry:

- Japan
- Non-Japan

**Adverse Events of Special Interest (AESI)**

As per ICH guidance (E2F Development Safety Update Report [2011]), the sponsor has identified the following AESIs for the ZX008 in below Table 6.

Table 6 – Adverse Events of Special Interest:

CV/Respiratory

• Chest pain – any pain in sternal area that is described for example as crushing, burning, sharp, stabbing or dull.

• Dyspnea/shortness of breath – any signs of difficult or labored breathing unrelated to a

This document is confidential.

**Statistical Analysis Plan**

Sponsor: Zogenix International Limited; Protocol No.: ZX008 Study 2 (ZX008-1501 and ZX008-1502)

previous medical condition that has not worsened.

 
• Persistent cough – longer than 4 weeks without a confirmed identified pathogen (or any other persistent cough that the investigator feels is suspicious).
 

 
• Increase in blood pressure >30% from Screening blood pressure or a systolic pressure <math>\geq 140</math> mmHg after repeated measures during one visit. Blood pressure should be repeated at appropriate times within the visit.
 

 
• Jugular venous distention- visible bulging of the external jugular veins on either side of the neck
 

 
• New onset heart murmur
 

 
• Pulmonary rales – an abnormal respiratory sound heard during auscultation of the lungs, which is also described as a crackle.
 

 
• Tachycardia – a persistent HR >30% above the screening value and unrelated to exercise, exertion or anxiety. Heart rate should be repeated at appropriate times within the visit.
 

 
• Signs that could indicate right ventricular failure: 
 
• Peripheral edema
 
• Ascites
 
• Syncope
 
• Decompensated right ventricular failure – symptoms include shortness of breath, frequent coughing especially when lying flat, abdominal swelling and pain, dizziness, fainting, and fatigue
 
 
 

 
• Signs on ECHO indicative of potential valvulopathy 
 
1. valve regurgitation (aortic or mitral)
 
2. <math>\geq</math> mild valve regurgitation (tricuspid or pulmonary)
 
3. Mean Mitral valve gradient <math>\geq 4</math> mmHg
 
4. Mean Aortic valve gradient <math>\geq 15</math> mmHg
 
5. Mean Tricuspid valve gradient <math>\geq 4</math> mmHg
 
6. Mean Pulmonary valve gradient <math>\geq 21</math> mmHg
 
 
 


 
• Signs on ECHO indicative of pulmonary hypertension 
 
a. Tricuspid Regurgitation Jet velocity <math>> 2.8</math> msec with or without the following findings OR
 
b. One of the following findings in the absence of being able to measure Tricuspid Regurgitation Jet velocity: 
 
i. Change in right ventricle/left ventricle basal diameter ratio <math>> 1.0</math>
 
ii. Right ventricular acceleration time <math>< 100</math> msec
 
iii. Dilatation of the inferior caval vein (diameter <math>> 21</math> mm and <math>< 50\%</math> inspiratory decrease) and/or right atrium
 
iv. Change in the geometry of the interventricular septum in systole (flattening) with left ventricular eccentricity index <math>> 1.1</math> in systole and/or in diastole
 
v. Early diastolic pulmonary regurgitation velocity <math>> 2.2</math> m/sec
 
vi. Tricuspid Annular Plane Systolic Excursion below 18 mm or below Z-score – 2
 
 
 
 
 

Metabolic/Endocrine

 
• Elevated prolactin level <math>\geq 2x</math> above the upper limit of normal (ULN)
 

 
• Galactorrhea
 

 
• Gynecomastia
 

 
• Increase in fasting serum blood glucose <math>\geq 2x</math> ULN
 

 
• Hypoglycemia – serum blood glucose more than 20% below the glucose level on Day -1 value or more than 10% below LLN (reference range 60 – 140 mg/dL)
 

This document is confidential.

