**6.4.7 Doppler Echocardiography**

Color Doppler echocardiography (ECHO) will be conducted at a facility with experience for the subject’s age at Screening, Maintenance period (Visit 8), End of study (Visit 12), and Cardiac Follow-up (Visit 14). ECHO uses ultrasound technology to examine the heart or blood vessels. An ECHO uses high frequency sound waves to create an image of the heart while the use of Doppler technology allows determination of the speed and direction of blood flow by utilizing the Doppler effect. Predetermined standard guidelines on the proper evaluation of certain measurements, as well as abnormality thresholds, were constructed by the sponsor’s IPCAB prior to study initiation. These thresholds are provided in the below table:

Signs on ECHO indicative of potential Valvulopathy
 
 
• valve regurgitation (aortic or mitral)
 
• ≥ mild valve regurgitation (tricuspid, or pulmonary)
 
• Mean Mitral valve gradient ≥ 4 mmHg
 
• Mean Aortic valve gradient ≥ 15 mmHg
 
• Mean Tricuspid valve gradient ≥ 4mmHg
 
• Peak Pulmonary valve gradient ≥ 21mmHg
 
	
Normal Values for Children 2-18 years
 
 
• No regurgitation
 
• Mean Mitral valve gradient < 4 mmHg
 
• Mean Aortic valve gradient < 15 mmHg
 
• Mean Tricuspid valve gradient < 4mmHg
 
• Peak Pulmonary valve gradient < 21mmHg
 

-------------------------------------------------------------------------------------------------------------------------------------------------------------------------------------------------------------------------------------------------------------------------------------------------------------------------------------------------------------------------------------------------------------------------------	---------------------------------------------------------------------------------------------------------------------------------------------------------------------------------------------------------------------------------------------------------------------------------------------------------------------------------

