### 3.2.7 Alert Criteria

Echocardiographic alert criteria included:

- Valve regurgitation (aortic or mitral)
- $\geq$  moderate valve regurgitation (tricuspid or pulmonic)
- Mean mitral valve gradient  $\geq$  4 mmHg
- Mean aortic valve gradient  $\geq$  15 mmHg

- Mean tricuspid valve gradient  $\geq 4$  mmHg
- Peak pulmonic valve gradient  $\geq 21$  mmHg
- Tricuspid regurgitation jet velocity  $> 2.8$  meters/sec with or without the findings OR
- One of the following findings in the absence of being able to measure tricuspid regurgitation jet velocity:
  - Change in right ventricle/left ventricle basal diameter ratio  $> 1.0$
  - Right ventricular outflow tract flow acceleration time  $< 100$  msec
  - Dilation of the inferior cava vein (diameter  $> 21$ mm and  $< 50\%$  inspiratory collapse) and/or right atrial dilatation
  - Change in the geometry of the interventricular septum in systole (flattening) with left ventricular eccentricity index  $> 1.1$  in systole and/or in diastole
  - Early diastolic pulmonary regurgitation velocity  $> 2.2$  m/sec
  - Tricuspid Annular Plane Systolic Excursion below 18 mm or below Z-score - 2

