**Statistical Analysis Plan**

Sponsor: Zogenix International Limited; Protocol No.: ZX008 Study 2 (ZX008-1501 and ZX008-1502)

Neuropsychiatric
1. Serotonin syndrome (At least 3 of following symptoms must be present: Agitation, restlessness, confusion, both increased HR and blood pressure, dilated pupils, muscle twitching, muscle rigidity, hyperhidrosis, diarrhea, headache, shivering, tremors, both nausea and vomiting)
2. Hallucinations
3. Psychosis
4. Euphoria
5. Mood disorders: depression and anxiety if they rise to a level of a disorder
6. Suicidal thoughts, ideation or gestures
Genitourinary
1. Priapism

MedDRA SMQs will be employed as applicable to identify each AESI category or manually assigned through review. This will be completed and documented prior to study unblinding.

Adverse events of special interests will be summarized by treatment group and by system organ class and preferred term for the T+M Period.

All adverse events of special interest will listed separately.

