#### **10.7. Doppler Echocardiography**

Color Doppler echocardiography (ECHO) will be conducted at a facility with experience for the subject's age at Screening, Maintenance period (Visit 8), End of study (Visit 12), and Cardiac Follow-up (Visit 14). ECHO uses ultrasound technology to examine the heart or blood vessels. An ECHO uses high frequency sound waves to create an image of the heart while the use of Doppler technology allows determination of the speed and direction of blood flow by utilizing the Doppler effect. Predetermined standard guidelines on the proper evaluation of certain measurements, as well as abnormality thresholds, were constructed by the sponsor's IPCAB prior to study initiation. These thresholds are provided in Cardiovascular SAP.

Results of ECHOs will be presented in a separate report from ERT.

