**Statistical Analysis Plan**

Sponsor: Zogenix International Limited; Protocol No.: ZX008 Study 2 (ZX008-1501 and ZX008-1502)

Table	14.3.1.2b	Treatment-Emergent Adverse Events by MedDRA System Organ Class and Preferred Term (Non-Japan) – Safety Population
Table	14.3.1.3	TEAEs Leading to Study Discontinuation by Primary SOC and PT – Safety Population
Table	14.3.1.3a	TEAEs Leading to Study Discontinuation by Primary SOC and PT (Japan) – Safety Population
Table	14.3.1.3b	TEAEs Leading to Study Discontinuation by Primary SOC and PT (Non-Japan) – Safety Population
Table	14.3.1.4	Serious TEAEs by Primary SOC and PT – Safety Population
Table	14.3.1.4a	Serious TEAEs by Primary SOC and PT (Japan) – Safety Population
Table	14.3.1.4b	Serious TEAEs by Primary SOC and PT (Non-Japan) – Safety Population
Table	14.3.1.5	Related TEAEs by Primary SOC and PT – Safety Population
Table	14.3.1.5a	Related TEAEs by Primary SOC and PT (Japan) – Safety Population
Table	14.3.1.5b	Related TEAEs by Primary SOC and PT (Non-Japan) – Safety Population
Table	14.3.1.6	TEAEs by Maximum Severity by SOC and PT– Safety Population
Table	14.3.1.6a	TEAEs by Maximum Severity by SOC and PT (Japan) – Safety Population
Table	14.3.1.6b	TEAEs by Maximum Severity by SOC and PT (Non-Japan) – Safety Population
Table	14.3.1.7	Treatment-Emergent Adverse Events Occurring in $\geq 5\%$ of Subjects by MedDRA System Organ Class and Preferred Term - Safety Population
Table	14.3.1.7a	Treatment-Emergent Adverse Events Occurring in $\geq 5\%$ of Subjects by MedDRA System Organ Class and Preferred Term (Japan) - Safety Population
Table	14.3.1.7b	Treatment-Emergent Adverse Events Occurring in $\geq 5\%$ of Subjects by MedDRA System Organ Class and Preferred Term (Non-Japan) - Safety Population
Table	14.3.1.8	Overview of Number of Subjects with Treatment-Emergent Adverse Events of Special Interest – Safety Population
Table	14.3.1.8a	Overview of Number of Subjects with Treatment-Emergent Adverse Events of Special Interest (Japan) – Safety Population
Table	14.3.1.8b	Overview of Number of Subjects with Treatment-Emergent Adverse Events of Special Interest (Non-Japan) – Safety Population
Table	14.3.1.9	Treatment-Emergent Adverse Events of Special Interest (AESI) by SOC and PT – Safety Population
Table	14.3.1.9a	Treatment-Emergent Adverse Events of Special Interest (AESI) by SOC and PT (Japan) – Safety Population

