### 3.2.5 Variables Measured

Echocardiograms were evaluated by two cardiologists using DigiView software. Details of the assessment and adjudication process are available in the ECHO operations manual for these studies.

In addition to assessing each valve (Mitral, Aortic, Tricuspid, and Pulmonary) for regurgitation, the following variables were measured or calculated on each ECHO:

- Right Ventricular Outflow Tract Acceleration Tim (RVOT)
- Pulmonary Artery Systolic Pressure (PASP)
- Pulmonic Valve Peak Regurgitation Jet Velocity (PVPR)

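### The Study 2 AESI table sets the 21 mmHg pulmonary valve limit on the mean gradient, while the advisory board's table and both cardiovascular SAPs set it on the peak

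*SAP*

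**What the plan says.** Table 6 in section 10.3 of the Study 2 SAP defines the AESIs. Its last item under signs of potential valvulopathy is "Mean Pulmonary valve gradient" at or above 21 mmHg. Table 5 in section 6.4.2 of the Study 1 SAP has the same entry.

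Three other lists use the peak:

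- Section 6.4.7 of the Study 1 SAP says that the sponsor's cardiology advisory board set the abnormality thresholds before the study began, and adds "These thresholds are provided in the below table". That table has "Peak Pulmonary valve gradient" at or above 21 mmHg as a sign of valvulopathy and a peak below 21 mmHg as normal.
- Section 3.2.7 of the Study 1 cardiovascular SAP has "Peak pulmonic valve gradient" with the same number.
- Section 3.2.7 of the Study 2 cardiovascular SAP has the same peak entry.

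The AESIs are counted in Study 2 Table 14.3.1.8, "Overview of Number of Subjects with Treatment-Emergent Adverse Events of Special Interest", and by preferred term in Table 14.3.1.9. On identifying AESIs by standardised MedDRA queries or manual review, section 10.3 says "This will be completed and documented prior to study unblinding".

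Separately, the Study 2 cardiovascular SAP gives cuts for the change in pulmonary artery systolic pressure (PASP) in more than one place. Section 2.3.2.2 and the title of Table 6.6 use more than 10, 15 and 20 mmHg. Section 4.5.2 uses 5, 10 and 15 mmHg.

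**The concern.** The number 21 is the same in all five lists, but the quantity it applies to is not. Mean and peak gradient are different measurements of one jet, and one cut-off cannot serve as the same limit for both. Set on the mean, the limit is the laxer of the two.

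At stake is whether a pulmonary valve that the board's table calls abnormal falls inside the AESI definition. No planned table in the Study 2 cardiovascular SAP reports valve gradients, so another table would not make good an omission from the AESI counts. Valve disease is the central safety question for this drug, and its definitions should agree across the documents before unblinding.

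**Working it through.** There is no stated figure to reproduce. The check sets the lists side by side (all limits are at or above the value shown, in mmHg).

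| List | Mitral | Aortic | Tricuspid | Pulmonary |
|---|---|---|---|---|
| Study 1 SAP, Table 5 (AESI) | mean 4 | mean 15 | mean 4 | **mean** 21 |
| Study 1 SAP, 6.4.7 (board) | mean 4 | mean 15 | mean 4 | **peak** 21 |
| Study 1 cardiovascular SAP, 3.2.7 | mean 4 | mean 15 | mean 4 | **peak** 21 |
| Study 2 SAP, Table 6 (AESI) | mean 4 | mean 15 | mean 4 | **mean** 21 |
| Study 2 cardiovascular SAP, 3.2.7 | mean 4 | mean 15 | mean 4 | **peak** 21 |

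1. Entries: 4 valves × 5 lists = 20.
2. Mitral, aortic and tricuspid: 3 × 5 = 15 entries, and all 15 agree in label and value.
3. Pulmonary: 5 entries, all at 21 mmHg. The label is mean in 2 (the two AESI tables) and peak in 3 (the board's table and the two alert lists).
4. Direction: a mean gradient cannot exceed the peak of the same jet. Every valve with a mean of at least 21 therefore also has a peak of at least 21, but not the reverse. The valves with peak ≥ 21 and mean < 21 are abnormal under the board's table and outside Table 6 on this item.

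The pattern is what a copying slip would produce: three lines beginning with mean, then a fourth given the same word. That is a reading of the table and not something the documents state.

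PASP cuts in the Study 2 cardiovascular SAP: {10, 15, 20} in section 2.3.2.2 and Table 6.6, and {5, 10, 15} in section 4.5.2. Shared: {10, 15}. Only in 4.5.2: {5}. Only in 2.3.2.2 and Table 6.6: {20}. No listed table title names a 5 mmHg cut. Table 7 is a categorical summary of echo differences from baseline and could hold one, but its title gives no cuts.

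**The case against.** Several points on the other side stand and limit the size of this one.

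- Section 10.3 describes no programmed gradient rule. AESIs are identified by standardised queries or assigned by manual review, so a reviewer may still include a valve that the written limit would exclude.
- A peak of at least 21 mmHg meets the central alert criteria, so the finding is not invisible. Raw echo data are also listed by subject and visit in Listing 2.1, although whether gradients are printed there is not stated. Section 3.2.5 does not name gradients where it says "the following variables were measured or calculated on each ECHO". That list is not exhaustive, however: section 3.2.6 compares readers on ejection fraction and fractional shortening, which it also omits.
- Section 10.3 attributes the AESI list to the sponsor, not to the board, and the protocol is not at hand. The board's table supports peak as the intended limit but does not settle what the sponsor meant.

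A reader might go further and infer that three safety thresholds in the Study 2 plans are wrong. The documents do not support that.

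- **The reference in section 10.7.** The Study 2 SAP describes guidelines that, "as well as abnormality thresholds, were constructed by the sponsor"'s advisory board, and refers to the cardiovascular SAP for the thresholds. It names no section and no alert list. The alert list there has at least moderate tricuspid or pulmonic regurgitation, where the board's table and Table 6 have at least mild, but an alert grade may properly differ. No count changes: Table 6 keeps at least mild, and the cardiovascular SAP tabulates tricuspid and pulmonic scores by visit (Tables 4.1.3 and 4.1.4) and at least mild at end of study (Tables 6.5.1 and 6.5.2).
- **The PASP cuts.** Neither set is shown to be wrong. Section 2.3.2.2 and Table 6.6 count a change at any time during therapy. Section 4.5.2 refers to each time point and may describe a separate by-visit summary. The mismatch is real, but it calls for clarification.

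**Conclusion.** The mean-versus-peak discrepancy holds on the text. As written, the AESI definition is laxer than the board's threshold for the pulmonary valve. The conclusion rests on two things: the five lists as printed, and the fact that a mean gradient is lower than the peak of the same jet. That the limit should read peak also rests on the board's table being authoritative, which should be confirmed.

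The impact is low. The documents give no echo rates and no size for the gap between mean and peak, so no number of missed subjects can be given, and it may be none. Only safety classification is affected. Efficacy, the aortic and mitral criteria, and the FDA case definition of valvulopathy are untouched. The PASP mismatch is a minor consistency matter.

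**What to change.** Change the last valvulopathy item in Table 6 of the Study 2 SAP from mean to peak, keeping the limit of at least 21 mmHg. Confirm the board's definition first, and make the change before AESI assignment is fixed ahead of unblinding. The cost is one word and possibly a few more AESIs to review. Study 1 was reported in September 2017 and need not be re-reported for this.

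In the Study 2 cardiovascular SAP, either align the PASP cuts in section 4.5.2 with section 2.3.2.2 and Table 6.6 (more than 10, 15 and 20 mmHg), or state that section 4.5.2 describes a separate by-visit summary and name its table. Table 6.6 needs no row for more than 5 mmHg: under section 3.2.6 two readers may differ by up to 10 mmHg in PASP before adjudication. This costs one sentence.

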**Statistical Analysis Plan**

Sponsor: Zogenix International Limited; Protocol No.: ZX008 Study 2 (ZX008-1501 and ZX008-1502)

Neuropsychiatric
1. Serotonin syndrome (At least 3 of following symptoms must be present: Agitation, restlessness, confusion, both increased HR and blood pressure, dilated pupils, muscle twitching, muscle rigidity, hyperhidrosis, diarrhea, headache, shivering, tremors, both nausea and vomiting)
2. Hallucinations
3. Psychosis
4. Euphoria
5. Mood disorders: depression and anxiety if they rise to a level of a disorder
6. Suicidal thoughts, ideation or gestures
Genitourinary
1. Priapism

MedDRA SMQs will be employed as applicable to identify each AESI category or manually assigned through review. This will be completed and documented prior to study unblinding.

Adverse events of special interests will be summarized by treatment group and by system organ class and preferred term for the T+M Period.

All adverse events of special interest will listed separately.

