## Statistical Analysis Plan

Sponsor: Zogenix International Limited; Protocol No.: ZX008 Study 2 (ZX008-1501 and ZX008-1502)

---

Observed continuous laboratory data will be descriptively summarized by type of laboratory test/parameter by treatment group. Changes from baseline will also be presented for all continuous laboratory parameters by treatment group over time.

Categorical laboratory parameters will be summarized by presenting the number and % of subjects by visit and by treatment arm.

All laboratory values (including invalid values, reference ranges, and possible flags (low, high,)) will be presented in the subject data listings.

A listing of subjects with Potentially Clinically Significant (Extreme) laboratory results will be provided.

A listing of subjects with markedly extreme abnormal laboratory results will be provided, and additional explorations of the data may be conducted as warranted. Additionally, summaries of abnormal lab results by parameter will be provided to investigate changes in platelet count and prolactin in greater detail. The summaries include:

- Subjects with decrease ( $\geq 25\%$  from baseline) in Platelets count with normal platelet count at baseline
- Subjects with decrease ( $\geq 25\%$  from baseline) in Platelets count relative to baseline (whether normal or abnormal) platelet count
- Subjects with increase ( $\geq 25\%$  from baseline) in prolactin with normal baseline
- Subjects with increase ( $\geq 25\%$  from baseline) in prolactin with normal baseline, and had seizure event within 48 hours prior to prolactin

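### The blood pressure, heart rate, prolactin and glucose AESIs have numeric limits, but no planned output applies those limits to the recorded values

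*SAP*

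**What the plan says.** **Definitions.** Table 6 in Section 10.3 of the Study 2 SAP sets these limits for vital signs and laboratory values:

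- Blood pressure: "Increase in blood pressure >30% from Screening blood pressure or a systolic pressure" of at least 140 mmHg "after repeated measures during one visit".
- Heart rate: a persistent rate more than 30% above the screening value, "unrelated to exercise, exertion or anxiety. Heart rate should be repeated at appropriate times within the visit".
- Prolactin: at least twice the upper limit of normal (ULN).
- High glucose: fasting glucose at least twice ULN.
- Hypoglycaemia: "serum blood glucose more than 20% below the glucose level on Day -1 value or more than 10% below LLN", with a stated reference range of 60 to 140 mg/dL.

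Table 5 in Section 6.4.2 of the Study 1 SAP has the same limits.

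**Identification.** Both SAPs give one rule: "MedDRA SMQs will be employed as applicable to identify each AESI category or manually assigned through review". The work is to be finished and documented before unblinding. Neither SAP says what is reviewed.

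**Output.** "Adverse events of special interests will be summarized by treatment group and by system organ class and preferred term for the T+M Period". The matching entry in the Study 2 index, Table 14.3.1.9, is "Treatment-Emergent Adverse Events of Special Interest (AESI) by SOC and PT – Safety Population". Table 14.3.1.8 is an overview of the same treatment-emergent events.

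**Other uses of the measured data.** Section 10.4 of the Study 2 SAP counts increases of at least 25% "in prolactin with normal baseline", and plans a listing of extreme laboratory results without linking its limits to Table 6. Section 10.5 plans a table of vital-sign abnormalities and leaves the limits to the sponsor.

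**The concern.** An AESI with a numeric limit invites the reader to take its count as the number of children who met the limit. The planned counts do not measure that. SMQs search coded adverse event terms, and a table by system organ class and preferred term can show only what exists as a coded event. A blood pressure or prolactin value has no preferred term until someone enters an event.

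Two errors follow. A child whose recorded value meets the limit, but for whom no event was entered, is missing from the AESI tables. A child with a coded term such as raised blood pressure may be counted although the limit was not met. The AESI counts for these items would then partly reflect reporting practice at the sites, and the comparison between arms would be harder to interpret. The manual review cannot be assumed to close the gap, because the SAP does not say that it covers the vital-sign or laboratory datasets.

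**Working it through.** There is no stated figure to reproduce. The check compares the definitions with the outputs and then does arithmetic on the SAP's own limits.

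**1. Does any output apply the limits to recorded values?** (Study 2 SAP)

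| AESI item | Limit in Table 6 | Nearest output from measured data | Same limit? |
|---|---|---|---|
| Blood pressure | >30% above Screening, or systolic ≥140 mmHg on repeat | Section 10.5: mean changes; abnormality table with limits left to the sponsor | Not stated |
| Heart rate | persistent, >30% above screening, not explained by exertion or anxiety | Section 10.5 as above; cardiovascular SAP 2.3.1.2: ECG rate by age band and change >20 bpm | No |
| Prolactin | ≥2 × ULN | Section 10.4, Tables 14.3.4.12 and 14.3.4.13: rise ≥25% from a normal baseline | No |
| High glucose | fasting, ≥2 × ULN | Section 10.4: descriptive summaries and extreme-value listing | Not stated |
| Low glucose | >20% below Day -1, or >10% below the lower limit of normal (LLN) | as for high glucose | Not stated |

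**2. Can a child meet a limit without there being an adverse event to enter?** Section 10.3 brings laboratory findings into the adverse event definition when they are abnormal and clinically significant. The inputs from Table 6 are LLN = 60 mg/dL and upper end of range = 140 mg/dL.

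- Absolute part: 0.9 × 60 = 54 mg/dL, so a value must be below 54.
- Relative part: a value must be below 0.8 × Day -1 glucose. This cut-off reaches the LLN when 0.8 × D = 60, so D = 60 / 0.8 = 75 mg/dL.
- D = 100 gives a cut-off of 0.8 × 100 = 80 mg/dL. D = 140 gives 0.8 × 140 = 112 mg/dL.

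Any Day -1 value above 75 mg/dL therefore lets a child meet the AESI limit at a value inside the reference range. Such a value need not be abnormal or clinically significant, so it need not become an adverse event. The two definitions can diverge, and the AESI tables follow the adverse event one.

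**3. Does the prolactin table fill the gap?** From a baseline at or below ULN to 2 × ULN is a rise of at least (2 − 1) / 1 = 100%. These children fall inside the ≥25% table but are not separated in it. From a baseline of 0.8 × ULN or less, a 25% rise gives at most 1.25 × 0.8 = 1.0 × ULN, so that table also counts children still within the normal limit. Children whose baseline was already high are outside it.

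**4. Is the method foreign to this SAP?** No. For status epilepticus, Section 8.2.2 of the Study 2 SAP combines adverse event records with diary seizures longer than 10 minutes, checks the overlap, and tabulates a combined count. The vital-sign and laboratory AESIs have no such step.

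**The case against.** The strongest objection is that the limits may be applied when the data are captured. The schedule of assessments has a row for AESIs separate from the one for adverse events. Table 6 also reads in places as an instruction to sites, for example on repeating blood pressure. If the protocol requires an event to be entered whenever a limit is met, most of these children are already in the adverse event data. The protocol is not at hand, so this stands as a limit on how large the gap can be said to be. It does not remove the gap: checking that rule against the data and tabulating the result is an analysis step, and the SAP has none.

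The values are also not lost from the report. Vital signs and laboratory results are summarised and listed, and the most abnormal laboratory values have their own tables. What is missing is a count against the stated limits.

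Part of the remedy needs judgement. Persistence and cause of a raised heart rate cannot be derived by program, the systolic limit needs repeat readings, and the laboratory list in Section 10.4 names glucose without fasting status. The in-range glucose example may also show that the Table 6 rule is broad. That does not explain why its result goes uncounted.

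Four stronger readings are tempting, and the documents do not support them:

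- **The manual review is confined to adverse event terms.** The SAP leaves its object open. The fault is that it is unspecified.
- **AESI incidence is understated.** Missed children lower the count and terms that do not meet the limit raise it, so the net direction is unknown.
- **A size can be put on the loss.** No reporting rate is given, and any figure would be an assumption.
- **Cardiac safety goes unmeasured.** The cardiovascular SAP for Study 2 counts valve regurgitation, pulmonary artery pressure and ECG heart-rate categories from measured data.

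**Conclusion.** The point holds for the blood pressure, heart rate, prolactin and glucose items. The SAP gives them numeric limits, identifies them through SMQs or an unspecified review, reports them only as coded events, and plans no output that states it applies the limits to the recorded values. The Study 1 SAP has the same identification rule and the same form of AESI table, without the ≥25% prolactin counts.

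It is a defect of the descriptive safety reporting. It touches no primary or key secondary inference, and Section 10.3 rules out p-values for adverse events. How many children are affected, and in which direction the arm comparison moves, cannot be determined from the SAP. The conclusion rests on the SAP text alone and would weaken in practice, though not in principle, if the protocol obliges sites to enter an event each time a limit is met. The ECHO items of Table 6 are outside the point.

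**What to change.** Keep the AE-based AESI tables and state which data the manual review covers. Add counts by arm of subjects meeting each limit at any time in T+M, derived from the laboratory and vital-sign datasets and shown beside the AE-based counts:

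- prolactin ≥2 × ULN, whatever the baseline;
- glucose >20% below Day -1, and glucose >10% below LLN, in separate rows;
- glucose ≥2 × ULN, with fasting status noted where known;
- blood pressure >30% above Screening, and systolic ≥140 mmHg, in separate rows, using repeat readings where recorded;
- heart rate >30% above Screening, labelled only as numeric threshold met, because persistence and cause need judgement.

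The limits are those already in Table 6, and no new assessments are needed. The cost is a few lines of SAP text and one or two descriptive tables. The drawback is that the 20% glucose row may include values within the reference range. Keeping it apart from the LLN row makes that visible.
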